5.2 Visit procedures

Below is a detailed description of each visit planned for the study. The Principal Investigator and/or his delegates will record each information first in the patient's medical record (or appropriate source document) and then in the eCRF.

Visit 1 (Screening): Day -90 to -1

- Informed Consent procedure completion, which has to be implemented before any trial procedures is performed
- Inclusion and exclusion criteria verification and confirmation
- Complete medical history, vital signs (BP, HR) collection and physical examination
- Pregnancy test (by serum or urine determination, according to Principal Investigator or hisdelegates decision) for women of childbearing potential or with amenorrhea ≤ 2 years
- Hematology examinations, which include: glucose, urea nitrogen, , creatinine, sodium, potassium, calcium, total
 cholesterol, HDL and LDL, triglyceride, , alkaline phosphatase, LDH, complete blood cell counts with differential and
 platelet counts, APTT, PT, INR, fibrinogen, VES, PCR
- ECG
- Pulmonary slab. In case the patient has performed a CT scan or RMN (because of the routinary assessment of the progression of the underlying disease) within at least 2 months from the ICF signature, the pulmonary slab will not be performed Liver function test includes: ALT, AST, ALP, bilirubin and total protein, Gamma-GT
- The determination of viral titres include: hepatitis B and C,. Tests to be performed only if not yet available within the medical history of the patient or if the relevant results need to be confirmed. HIV test is performed according to Principal Investigator or his delegates decision
- Concomitant medications recordings
- · Adverse event assessment and recording

Visit 2 (Baseline):- Day 0

- Laboratory test results evaluation
- Check and confirmation of the inclusion and exclusion criteria vs. the laboratory test results
- Randomization of the patient, according to the specific procedure implemented for the study
- Concomitant medications recordings
- · Adverse event assessment and recording

Visit 3 (Surgery):Day 1

- Evaluation of the appropriate target bleeding site in the hepatic parenchyma ("oozing" or "moderate")
- Recording of bleeding site characteristics (source of bleeding, bleeding severity using "oozing" or "moderate", approximate area of bleeding site)
- Recording of intraoperative details (hepatic parenchyma characteristics, intraoperative measurement of total

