 volume of transfused blood products, duration of the surgery, type of hepatic resection, the estimated
 intraoperative blood loss and the use of Pringle's maneuver) Concomitant medications recordings
- Adverse event (intraoperative and not-intraoperative) assessment and recording

The patients randomized to Common Surgical Techniques (CST) will be treated conventionally while the patients randomized to experimental technique (CST + Hemopatch) will be treated conventionally with the adjunct of Hemopatch.

For patients included in ARM B Hemopatch is applied upon the verification made by the surgeon of the presence of an appropriate target bleeding (oozing or moderate) site in the hepatic parenchyma. At the time point of application a stopwatch starts simultaneously (time zero). Time to hemostasis is defined as the time required to obtain successful haemostasis in a single bleeding site. This time will be recorded by the operator delegated by the Principal Investigator and according to the surgeon's observation. At 3 minutes the inspection will be made and, if haemostasis is not

achieved, the treatment is considered failed and the Principal Investigator and/or his delegates is allowed to use additional haemostatic measures (including other topical haemostatic agents).

The time to haemostasis will be recorded before in the patient's medical record and then in the eCRF. The bleeding site will be observed for 1 additional minute (after the first 3 minutes) at the end of the haemostatic procedure and at the end of the surgery, in order to confirm the achievement of haemostasis. At the end of surgery at least one perihepatic Jackson-Pratt drain will be left near the site of resection.

Patients allocated to ARM A, will undergo the conventional hemostatic procedures and therefore also these patients will end up with a perihepatic Jackson-Pratt drain, which will be left near the site of resection.

Visit 4 (+1 day after Surgery): Day 2

- Hematology examinations, which includes: glucose, urea nitrogen, creatinine, sodium, potassium, calcium, total
 cholesterol, HDL and LDL, triglyceride, alkaline phosphatase, LDH, complete blood cell counts with differential and
 platelet counts, APTT, PT, INR, fibrinogen, VES, PCR
- · Liver function test examinations, which include: ALT, AST, ALP, bilirubin and total protein, gamma-GT
- Output (in ml) and characteristics of the perihepatic drains (drain pigmentation, i.e. biliary bloody clear)

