7. STUDY TREATMENT

7.1 Treatment in study

Hemopatch is an EMA approved sealant for hemostasis. It consists of a soft, thin, pliable, flexible pad of collagen derived from bovine dermis, coated with NHS-PEG. The white, tissue-facing side is covered with a thin layer of NHS-PEG that provides firm tissue attachment, thus sealing the bleeding surface and inducing hemostasis simultaneously. Due to its flexible structure, the application of Hemopatch to the site where hemostasis is desired is easily controlled. For differentiation, the non-coated side is marked with blue squares of a biocompatible colorant.

Hemopatch will be supplied in the following size:

Hemopatch 45 x 90 mm

Hemopatch is intended as an haemostatic device for surgical procedures when control of bleeding by pressure, ligature or conventional procedures is either ineffective or impractical.

In contact with blood, collagen induces aggregation of platelets. Platelets deposit in large numbers on the collagen structure, degranulate, and release coagulation factors that, together with plasma factors, enable the formation of fibrin. The structure of Hemopatch provides a three dimensional matrix for the additional mechanical strengthening of the clot. The NHS-PEG coating of this device, when in contact with blood, enhances its tissue adhesion properties and seals the bleeding surface. When applied as recommended, Hemopatch is resorbed in 6 – 8 weeks with little tissue reaction.

Hemopatch is not intended to be used in pulsatile, severe bleedings. The use of Hemopatch is not recommended in the presence of an active infection. Hemopatch is not intended as a substitute for meticulous surgical technique and the proper application of ligatures or other conventional procedures for hemostasis. Hemopatch should be maintained dry prior to application [15].

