7.1.1 Application of Hemopatch

The investigator will select the appropriate size of the pad so that it overlaps the margins of the bleeding surface by about 1 cm. The pad may be cut to the desired size and shape. Dry gloves and surgical instruments (forceps, scissors) should be used to handle, cut and apply Hemopatch. Multiple pads may be used for larger bleeding surfaces. The investigator will apply the dry Hemopatch with the non-marked white surface contacting the bleeding area. A dry gauze or patty will be used and will be hold in place with gentle, uniform pressure over the entire pad surface for 2 minutes. When applying Hemopatch, the investigator should minimize contact with bloody surgical instruments, gauzes or gloves due to the affinity of collagen to blood. After 2 minutes, the investigator should gently remove the gauze or patty from the pad; gentle irrigation may also help in removing the gauze or patty without dislodging Hemopatch from the bleeding site. If the bleeding has not been satisfactorily controlled, Hemopatch can be removed, without tissue damage, up to 3 minutes from the time of the initial tissue contact. The investigator should not try to forcefully remove the pad.

The target bleeding site is defined as a bleeding site that, after 30 seconds of firm manual compression, has persistent bleeding requiring immediate attention. The investigator, an experienced hepatic surgeon, will define the bleeding source (arterial, venous, capillary), bleeding severity (oozing, middle or spurting) and the approximate area of bleeding site (cm², mean).

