11.2 Analysis populations

For this study, two populations will be considered:

Safety population defined as all patients who signed the Informed Consent. This population will be used for the safety and tolerability analyses.

Intention-To-Treat (ITT) population defined as all the randomized patients who received the assigned treatment. This population will be used for the efficacy analyses.

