11.5 Efficacy analyses

Responder definition

A patient is defined as "Responder" if he/she achieves hemostasis after 3 min. Time to haemostasis is defined as the time required to obtain successful haemostasis in a single bleeding site. At 3 min, the inspection will be made and, if haemostasis is not achieved, the treatment is considered failed and the patient will be defined as "Non-Responder". A patient assigned to the experimental arm (Hemopatch) for whom was not possible, for any reason, to proceed with the assigned treatment (i.e. has to be treated with the standard care) will be considered as "Randomization failure" and excluded from the ITT population.

In accordance with the primary objective of the study, the proportion of responder patients measured at treatment end (i.e. visit 3) will be the primary endpoint.

The treatment comparison will be performed by a χ^2 test.

The test will be two-sided and conducted at the standard 0.05 significance level

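### Section 11.5 drops from the primary analysis, in Arm B only, randomized patients who could not receive Hemopatch, and still calls the set ITT

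*Protocol*

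**What the plan says.** - **Who is removed.** Protocol 11.5 defines the Randomization failure as an Arm B patient "for whom was not possible, for any reason, to proceed with the assigned treatment (i.e. has to be treated with the standard care", and excludes that patient from the ITT population.
- **Which set is analysed.** Protocol 11.2 describes the ITT population as "defined as all the randomized patients who received the assigned treatment" and uses it for efficacy, so it governs the primary χ² test.
- **When the decision falls.** Under 7.2, allocation is made at visit 2, before surgery, and is hidden from patients but not from physicians. At visit 3, "Hemopatch is applied upon the verification made by the surgeon of the presence of an appropriate target bleeding (oozing or moderate) site" (5.2). Section 7.1 adds that "Hemopatch is not intended to be used in pulsatile, severe bleedings".
- **What counts as failure.** Protocol 11.5 also states: "At 3 min, the inspection will be made and, if haemostasis is not achieved, the treatment is considered failed". That patient is a Non-Responder and stays in.

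**The concern.** Whether an Arm B patient is analysed depends on a judgement made during surgery, by someone who knows the allocation, about a feature (the bleeding) that also predicts the outcome. An operated Arm A patient with the same bleeding has received common surgical techniques and so stays in. The χ² test then compares Arm A as operated with an Arm B group selected after randomization.

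The bias can go either way. If the excluded patients bled too heavily for a pad, Arm B loses likely failures and the comparison favours Hemopatch. If they had no qualifying bleeding, and similar Arm A patients are scored as Responders, Arm B loses likely successes and the comparison is tilted against it. In both cases the set labelled ITT no longer has the protection of randomization.

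**Working it through.** **Inputs from the Protocol.** Response 66% and 34%, power 90%, significance level 5%, 49 per arm (11.1); two-sided χ² test (11.5).

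**Assumptions.** The share s of Arm B that is excluded (5% or 10%, i.e. 2.5 or 4.9 of 49 patients) and the proportion r of those who would have been dry at 3 minutes. The protocol gives neither. Comparable Arm A patients are assumed to stay in.

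**Step 1: the plan's sample size.** With pooled variance, n per arm = [1.96·√(2·0.5·0.5) + 1.2816·√(0.66·0.34 + 0.34·0.66)]² / 0.32² = (1.386 + 0.859)² / 0.1024 = 49.2. The stated 49 per arm is reproduced apart from rounding. Exact power of the uncorrected χ² test at 49 per arm is 0.905. The sample size is not in dispute.

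**Step 2: type I error under the rule.** No true effect, 34% in both arms. Arm A ~ Bin(49, 0.34). The analysed Arm B size is n ~ Bin(49, 1 − s), with response rate (0.34 − r·s)/(1 − s). All outcomes are enumerated exactly. Without exclusions the two-sided error is 0.048, of which 0.024 favours Hemopatch.

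| Excluded patients dry at 3 min (r) | s | Arm B rate analysed | Two-sided error | Part favouring Hemopatch |
|---|---|---|---|---|
| 0% (too severe for a pad) | 5% | 0.34/0.95 = 0.358 | 0.054 | 0.038 |
| | 10% | 0.34/0.90 = 0.378 | 0.067 | 0.057 |
| 17% (half the usual rate) | 5% | 0.3315/0.95 = 0.349 | 0.051 | 0.031 |
| | 10% | 0.323/0.90 = 0.359 | 0.055 | 0.039 |
| 100% (no real bleeding) | 5% | 0.29/0.95 = 0.305 | 0.066 | 0.010 |
| | 10% | 0.24/0.90 = 0.267 | 0.119 | 0.003 |

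As a check, r = 34% leaves the Arm B rate at 0.34, and the same enumeration gives 0.050 at both shares. Exclusion unrelated to outcome does no harm; the selection does.

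**Step 3: when a single result would change.** Against Arm A 17/49, Arm B 26/49 gives p = 0.067. With two Arm B non-responders excluded, 26/47 gives p = 0.042. Near the planned rates, 32/49 against 17/49 gives p = 0.002. Taking out five Arm B responders leaves 27/44: z = (0.6136 − 0.3469)/√[0.473·0.527·(1/44 + 1/49)] = 2.57, p = 0.010. Only results near the threshold depend on the rule.

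**Step 4: power if these patients are kept** (66% in those who get a pad, 49 per arm).

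| Never treated (s) | Excluded | Kept, respond at 34% | Kept, none respond |
|---|---|---|---|
| 5% | 0.889 | 0.873 (Arm B rate 0.644) | 0.832 (0.627) |
| 10% | 0.881 | 0.835 (0.628) | 0.733 (0.594) |

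**The case against.** **The 11.2 condition covers both arms.** On paper it does, so the absence of a matching rule is exact only for 11.5. In effect the asymmetry remains: Arm A's treatment is conventional haemostasis, and an operated patient meets the condition almost automatically.

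**The treatment of Arm A is partly inferred.** The visit 3 step "Evaluation of the appropriate target bleeding site in the hepatic parenchyma" applies to all patients, and the protocol does not say how an Arm A patient with no qualifying site, or with spurting bleeding, is scored. That objection stands. The table depends on such patients staying in, which is why it is conditional.

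**The extremes exaggerate.** With the 17% case the total error barely moves (0.051 or 0.055). That is fair, and no exclusion rate is documented.

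**The trial calls itself exploratory.** It still sizes and specifies a two-sided 0.05 test.

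**A stronger reading is tempting:** that pads which were applied and failed may also be excluded, since the rule says for any reason. A reader might also infer this from 6.3 and 8.1, which describe Hemopatch failures as withdrawn or dropped out. The text disfavours it. A patient with a pad applied has received the assigned treatment, no haemostasis at 3 minutes is a Non-Responder, and under 5.2 it is at that inspection that "the treatment is considered failed and the Principal Investigator and/or his delegates is allowed to use additional haemostatic measures". Sections 6.3 and 8.1 concern safety follow-up. What remains is a secondary ambiguity: 7.1.1 says "If the bleeding has not been satisfactorily controlled, Hemopatch can be removed, without tissue damage, up to 3 minutes", and 11.5 does not name the patient whose pad comes off before the inspection.

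**Conclusion.** The point holds for Arm B patients who never receive a pad. Protocol 11.5 fixes a post-randomization exclusion that operates in one arm, depends on an unblinded judgement linked to bleeding severity, and is mislabelled ITT. Because the protocol states the rule outright, it is not a detail left to the SAP.

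The size is modest and conditional. At 5% or 10% excluded, two-sided type I error lies between 0.051 and 0.119 against 0.048, depending on who is excluded. The part favouring Hemopatch lies between 0.003 and 0.057 against 0.024. The effect is zero if nobody is excluded, and a result at the planned rates would stand. A reader might infer that the rule always favours Hemopatch; the documents do not settle the direction. It should be fixed before the data are seen, because a result near the threshold could turn on two patients.

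**What to change.** **Change.**
1. In 11.5, delete the Arm B-only Randomization failure exclusion; in 11.2, delete the condition that the assigned treatment was received. State instead: All randomized patients are analysed in the arm assigned. A patient without haemostasis at the target bleeding site at 3 minutes is a Non-Responder, whether or not a pad was used.
2. If patients with no liver resection or no qualifying target bleeding site are to be left out, use one criterion, identical in both arms and based on the visit 3 evaluation already scheduled for everyone. Preferably record it before the surgeon learns the allocation.
3. State that a patient whose pad has touched the site is never a Randomization failure.
4. Keep the present set as a sensitivity analysis.

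**Cost.** Items 1, 3 and 4 are mainly wording. Section 5.2 starts the Arm B stopwatch at pad application, so a time zero must be named for an Arm B patient with no pad. Delaying disclosure until after the site evaluation would change procedure, since allocation is made at visit 2 and packages are assigned through it.

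The power loss should be stated plainly. At 5% or 10% never treated, power falls from 0.905 to 0.873 or 0.835 if those patients respond at 34%, and to 0.832 or 0.733 if none do. Restoring 90% by the pooled formula would need 110 or 124 patients in the first case, and 124 or 158 in the second, against 98. If the sponsor expects such patients to be rare, 98 can stand with the loss acknowledged.

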11.6 Safety analyses

The Safety population will be used to evaluate safety and tolerability data.

Physical examinations, vital signs, laboratory tests, adverse events and concomitant medications will be considered for the safety and tolerability evaluation.

Categorical variables (physical examination normality, etc.) will be analyzed with shift tables (baseline vs. last visit), while continuous variables (laboratory parameters, vital signs, etc.) by descriptive summaries.

Laboratory data will also be analysed with shift tables (baseline vs. last visit), considering each value as being normal/abnormal with respect to the appropriate normal ranges.

Baseline conditions and adverse events will be coded using the MedDRA dictionary. All the data related to the baseline conditions and adverse events will be listed by patient. Descriptive statistics will be performed classifying the events by system organ class and preferred term; they will also be classified by seriousness and relationship with the study treatment.

Prior and concomitant medications will be summarized using the WHO coding system.

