 - During the hospitalization (from day 2 to day 6) the panel of the blood tests could be modified.
- note 3: the assessment of liver function includes: ALT, AST ALP, bilirubin and total protein, gamma-GT,.

 During the hospitalization (from day 2 to day 6) the panel of the liver function could be modified.

- note 4: viral titres include: Hepatitis B and C. Tests to be performed only if not yet available within the medical history of the patient or if the previous results available have to be confirmed. HIV test is performed according to Principal Investigator or his delegates decision.
- note 5: hematology, the assessment of liver function, the determination of the viral titres and the pregnancy test, if applicable, will be evaluated by the Principal Investigator (PI) and/or his delegates and recorded first in the patient's medical record and then in the eCRF. The Principal Investigator and/or his delegates will check the laboratory test results vs. the inclusion/exclusion criteria. In case any result shows an out of range parameter judged to have an impact on the Inclusion/exclusion criteria, this will be repeated before the confirmation for randomization.
- note 6: randomization will be performed by an independent statistician who will maintain it during the entire period of the study.
- note 7: the Principal Investigator and/or his delegates will record, first in the patient's medical record and then in the eCRF, the following information: source of bleeding, bleeding severity using "oozing" or "moderate", approximate area of bleeding.
- note 8: the Principal Investigator and/or his delegates will record, first in the patient's medical record and then in the eCRF, the following information: hepatic parenchyma characteristics, intraoperative measurement of total volume of transfused blood products, duration of the surgery, type of the hepatic resection, the estimated intraoperative blood loss, the use of Pringle's maneuver.
- note 9: the Principal Investigator and/or his delegates will record, first in the patient's medical record and then in the eCRF, the output (in ml) and the characteristics of the perihepatic drains (drain pigmentation, i.e.biliary bloody clear). These information will be recorded by the Principal Investigator and/or his delegates from day 1 after surgery to the End of Study Visit if the drainage is still in place.

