- Output (in ml) and characteristics of the perihepatic drains (drain pigmentation, i.e. biliary bloody clear), if the drainage is still in place
- Timing of abdominal drainage removal, if applicable
- · Concomitant medications recordings
- · Adverse Event assessment and recording

Visit 8 (6-8 weeks after Surgery): End of Study Visit

- Hematology examinations, which includes: glucose, urea nitrogen, creatinine, sodium, potassium, calcium, total cholesterol, HDL and LDL, triglyceride, alkaline phosphatase, LDH, complete blood cell counts with differential and platelet counts, APTT, PT, INR, fibrinogen, VES, PCR
- Liver function test examinations, which include: ALT, AST, ALP, bilirubin and total protein, gamma-GT.
- Output (in ml) and characteristics of the perihepatic drains (drain pigmentation, i.e. biliary bloody clear), if the drainage is still in place
- Concomitant medications recordings
- · Adverse Event assessment and recording

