6.3 Withdrawal procedures

Patients have the right to withdraw from the trial on their request or at the discretion of the Principal Investigator and or his delegates.

The discontinuation from the study is foreseen in the following conditions:

- ✓ patient's request (also not motivated);
- ✓ principal investigator's decision (motivated) if considered as necessary, in own judgment, for the interest of the patient;
- ✓ occurrence of new diseases clinically relevant, not related to the study treatment;
- ✓ occurrence of particularly important adverse reactions;
- ✓ occurrence, in the course of the study, of one or more of the situations listed in the "exclusion criteria".

Patients withdrawn because of Hemopatch's failure, should be monitored for safety until the end of the study (please refer to the section 9.1).

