11.3 Methods

The analyses will be performed with SAS version 9.4. All the variables will be descriptively analyzed by treatment and visit (mean, median, standard deviation, minimum and maximum for continuous variables, frequency distribution for categorical variables).

All the analyses to be carried out will be detailed in the Statistical Analysis Plan (SAP) which will be finalized in Version 1.0 before the Data Base freezing. Version 2.0 of the SAP will be prepared after the Data Review Meeting (in which the protocol violations will be evaluated) and will include the list of the patients belonging to the defined populations and the randomization list.

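### The laboratory shift tables in section 11.6 compare baseline with the last visit only, so they cannot show patient-level shifts at Visits 4-7 that have resolved by then

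*Protocol*

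**What the plan says.** Protocol section 11.6 sets out two analyses of laboratory data. The first treats the parameters as continuous: "continuous variables (laboratory parameters, vital signs, etc.) by descriptive summaries". The second is the categorical one: "Laboratory data will also be analysed with shift tables (baseline vs. last visit", with each value classed as normal or abnormal against the normal ranges. Section 11.3 adds a general rule: "All the variables will be descriptively analyzed by treatment and visit (mean, median, standard deviation, minimum and maximum for continuous variables", with frequency distributions for categorical variables.

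The flow chart (section 5.1) and the visit descriptions (section 5.2) schedule hematology and liver function at screening and at five visits after surgery. The first of these is "Visit 4 (+1 day after Surgery): Day 2" and the last is "Visit 8 (6-8 weeks after Surgery): End of Study Visit". Notes to the flow chart allow the in-hospital panel to vary: "During the hospitalization (from day 2 to day 6) the panel of the blood tests could be modified", with a matching note for liver function.

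Last visit is not defined. Section 6.3 foresees early discontinuation for several reasons, among them "occurrence of particularly important adverse reactions". Section 11.2 defines the safety population as everyone who signed consent.

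**The concern.** The shift table is the only laboratory analysis in section 11.6 that follows each patient from normal to abnormal, and its post-operative time point is chosen, not left open. In a completer that time point is six to eight weeks after resection. A patient with a normal value before surgery, an abnormal one on Day 2 and a normal one at week 6-8 is tabulated as normal to normal.

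Reducing post-operative complications is a secondary objective (section 3.2), and the early post-operative period is where a difference between arms in, for example, INR or bilirubin would most plausibly appear. A shift table that looks only at the end of follow-up answers a different question: whether a change persists.

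A second difficulty is that the column may not refer to one time. If last visit means the last attended visit, a patient who dies or withdraws in hospital contributes a value from Day 2-6, next to week 6-8 values from everyone else.

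**Working it through.** The plan states no figure on this point to reproduce. The check sets the schedule against the rule.

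**1. Samples scheduled and samples used**

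| Visit | Time (section 5.1) | Hematology and liver tests | In the shift table for a completer |
|---|---|---|---|
| V4 | Day 2 | yes | no |
| V5 | Day 3 | yes | no |
| V6 | Day 4-6 | yes | no |
| V7 | Day 30 ± 2 | yes | no |
| V8 | 6-8 weeks | yes | yes |

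Used: 1/5 = 20%. Not used in this table: 4/5 = 80%.

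**2. What the by-visit summaries add**

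The rule in section 11.3 covers all five visits by arm. Mean, median and standard deviation describe the group, and the minimum and maximum each rest on one patient. None of them counts patients who moved from normal to abnormal. The frequency distributions that section 11.3 promises for categorical variables could be read as giving abnormal counts at each visit. But section 11.6 treats laboratory parameters as continuous and introduces normal/abnormal status only for the shift table. Even on the generous reading, a count of abnormal values at a visit does not separate new abnormalities from those present before surgery.

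**3. The two readings of last visit**

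- *Visit 8.* Patients who die or withdraw earlier are absent from the table. Nothing is mixed, but the number assessed is needed to read it.
- *Last available value.* Let d be the proportion whose last value is an early one, p_early the proportion abnormal soon after surgery and p_8 the proportion abnormal at week 6-8. The table shows (1 − d) × p_8 + d × p_early.

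The protocol gives none of these three quantities. Assuming p_early = 60% and p_8 = 10% for illustration:

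| d | Calculation | Abnormal at last visit |
|---|---|---|
| 0% | 1.00 × 10% + 0 × 60% | 10% |
| 5% | 0.95 × 10% + 0.05 × 60% | 12.5% |
| 10% | 0.90 × 10% + 0.10 × 60% | 15% |
| 20% | 0.80 × 10% + 0.20 × 60% | 20% |

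Under these assumptions, two arms with identical laboratory courses but 5% and 20% early exits would differ by 20% − 12.5% = 7.5 percentage points. This shows the mechanism and does not estimate its size in this trial.

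**4. Follow-up after withdrawal**

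Section 6.3 keeps patients withdrawn for Hemopatch failure under safety monitoring to the end of the study. The safety follow-up text in section 8.1 asks those dropped for failure with the patch left in place to attend Visits 4 to 8. Both provisions concern the Hemopatch arm. No equivalent is stated for other withdrawals or for the control arm, and no such rule can help with deaths. Mixing is therefore limited for one group and possible for the rest.

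**The case against.** The strongest reply is that the shift tables are an addition. Section 11.6 says laboratory data will *also* be analysed this way, the by-visit summaries cover every post-operative sample by arm, and a marked in-hospital difference would show in the median or maximum. Bile leaks, drainage volume, transfused volume and any adverse event are secondary endpoints in their own right (section 4.1). Drain bilirubin and ultrasound are done at Visit 5, and adverse events are assessed at every visit and listed by patient. All of this stands. A reader might infer that the plan hides acute post-operative abnormalities; it does not. What is missing is a clear patient-level categorical view of them.

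It can also be said that baseline against end of study is a legitimate comparison, since it looks for persistent change over the period in which the patch is resorbed. That stands too, and is a reason to keep that comparison alongside the early ones.

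A reader might take it as settled that early values from dropouts contaminate the last-visit column. The protocol does not say so. The flow chart names Visit 8 as the end of study visit, and a withdrawal reason in section 6.3 does not by itself mean that sampling stops.

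A reader might also infer that the Day 2-6 results are selectively missing. The notes say only that the panel could be modified. That justifies showing how many patients were assessed. It does not justify a fixed in-hospital core panel, which would constrain in-hospital testing and is not needed to repair the tables.

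Finally, analysis detail is deferred to a statistical analysis plan that is not shown, and it may define last visit or add tables. But section 11.6 states the comparison outright, and a plan that follows it literally would carry the gap over.

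**Conclusion.** The point holds as a modest one. As written, the laboratory shift tables use 1 of 5 scheduled post-operative samples in a completer and cannot show a shift at Visits 4-7 that has resolved by week 6-8. The by-visit summaries report those values but do not clearly count patients who moved from normal to abnormal. This part follows from the text and needs no assumption.

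The pooling of early with late values is conditional on last visit meaning last available value, and its size cannot be computed because the protocol gives no dropout or abnormality rates.

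It is also easy to build an example in which the arms differ sharply in hospital and the table shows nothing. If 20% and 40% of 49 patients were newly abnormal and all recovered, 9.8 against 19.6 patients (about 10 against 20) would appear as 0 against 0. Those rates and the complete recovery are assumed, and the example looks at the shift table alone, so it should not be taken as the size of the problem.

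This is one descriptive safety display in an exploratory trial. It touches neither the primary endpoint nor the sample size. The change is worth making because it is cheap.

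**What to change.** In section 11.6, replace the baseline-to-last-visit rule for laboratory data with:

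- shift tables by arm from baseline to each post-operative visit, V4 to V8;
- a shift table by arm from baseline to the worst post-operative value;
- the end-of-study shift at Visit 8 itself, among patients with a Visit 8 sample, which removes the undefined term;
- the number of patients assessed for each test at each visit, because the in-hospital panel may vary and the safety population includes everyone who consented.

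The cost is a change of wording and a few more descriptive tables from data already planned; no extra sample is needed. One limitation should be accepted openly. For tests that are abnormal in most patients right after resection, a binary worst-value shift will put many patients in both arms in the same cell and discriminate little. The by-visit shifts are therefore needed as well, and the worst-value table should not stand alone.
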